10.2. Sample size

As this is an exploratory clinical investigation no formal sample size calculation has been performed. It is assumed that 20 randomized subjects will be adequate for obtaining indications on performance and feasibility, and we aim to have an equal distribution between neurogenic and functional subjects.

10.3. Level of significance and power

For Fisher's Exact Test a one-side 5% test level will be applied. As this is an exploratory investigation no power has been applied, when evaluating the sample size. If other explorative statistical analyses are performed a significance level of 5% will be applied.

10.4. Pass/fail criteria

No formal success criteria are applied in this explorative clinical investigation.

10.5. Interim analysis

There is no planned interim analysis in this clinical investigation.

10.6. Statistical reason for termination of investigation

There will be no interim analysis and therefore no reason to terminate the investigation based on statistical considerations.

10.7. Deviations from statistical design, method or analytical procedures

Any deviations from the statistical plan will be documented in the clinical investigation report.

11. Data management

Data management of all measurements described in this protocol are carried out by Clinical Operations, Coloplast A/S.

Data will be collected through an electronic data capturing (EDC) system on eCRF, a secure, internet-based case report form.

The EDC system used is

The system is designed to be compliant with the FDA requirements of 21 CFR part 11. It is a validated data management system, with restricted role-based access control, allowing only qualified and trained personnel to enter the system. The system has full audit trail and electronic signature.

The PI and delegate(s), and investigation monitor(s) must be trained in the system prior to getting access. The training is web-based (eLearning) and must be completed before access to the investigation is granted. The web-based training will be documented in the data management system. In addition, the data management specialist will demonstrate the system on a virtual/physical meeting. This training will be documented in the Clinical Investigation Training Log. The sponsor will be responsible for training the investigator, delegate(s) and the monitor(s).

Only the principal investigator, or delegate(s), who have completed the relevant eLearning, signed the Site Personnel Signature and Delegation List and Clinical Investigation Training Log will be authorised to enter data in the eCRF.

The eCRF will be completed by the PI, or delegate, that will perform primary data collection directly into the eCRF or drawn from source-documents. The eCRF will be completed on a continuous basis starting from the point of enrolling the subject to final follow up. In addition, the PI, using his/her personal login information, will be authorised to, and must, sign each eCRF. It will also be the responsibility of the PI to ensure that all measurements and observations are correctly noted in the eCRF.

Clinical Investigation Plan_

The PI will keep a separate list of the subjects' ID numbers, names, and addresses in a locked room/cabinet.

The monitor, using his/her personal login information shall verify all data points and issue electronic queries for the authorised clinical site personnel to respond, as defined in the monitoring section (and monitoring plan, if created).

The Data Validation Plan describes which edit checks, range checks, and other consistence checks that will be done on the clinical data during conduct of the investigation. The Data Validation Plan will be developed in collaboration with the Clinical Manager and the Statistician and will be aligned with the monitoring section (and monitoring plan, if created).

A critical quality control will be performed by the data management team and queries issued where needed. Such queries must be resolved by the site personnel. Automated, real-time access to the data enable control on study compliance and safety assessments. A full audit trail ensures, that each user's (site personnel, monitor, sponsor, data manager) access to and actions in the system is tracked.

At the end of the study formal data review meeting(s) will be performed before the database will be locked.

The Data Management procedures are further described in the Data Management instructions.

11.1. Data collection procedure

All assessments and observations throughout the investigation for each subject must be carefully recorded in an eCRF or in a paper CRF (pCRF) during the visit or immediately after. The eCRF makes it possible to enter data right away when they are obtained. This is the preferred way of collecting data. In case this is not possible the data should be entered no later than seven days after the visit / procedure.

When subject and PI is required to complete different sections in the CRF, it will be specified which sections the subject will fill in (using paper CRF or app solution) and which sections the investigator will fill in.

In the unforeseen situation, where site cannot establish connection to the EDC system, a paper CRF (pCRF) has been printed and supplied by sponsor.

Other:

The remaining endpoints, assessment and baseline information can be entered directly into the eCRF.

11.2. Data retention

The Investigator file must be archived for a minimum period of 10 years after the final clinical investigation report has been signed.

12. Amendments to the Clinical Investigation Plan

No changes in the clinical investigation procedures shall be affected without mutual agreement between the principal investigator and the sponsor. The agreement of the changes must be documented by signing the corresponding clinical investigation plan amendments and registered in the Change Log.

All significant changes require notification to the EC/ and applicable regulatory authority. Substantial changes may require approval from the EC and applicable regulatory authority prior to implementation.

13. Deviations from the Clinical Investigation Plan

Deviations to the Clinical Investigation Plan occurs when the activities during the clinical investigation do not comply with the EC approved investigation plan.

The PI is not allowed to deviate from the Clinical Investigation Plan unless, under emergency circumstances or to protect the rights, safety, and welfare of the subject(s).

If a situation occurs, that affect the rights, safety and well-being of the subject(s), the PI is obliged to deviate from the CIP, and other regulations to protect the subject. The PI must inform the monitor immediately, and the Monitor will report and inform the Clinical Manager or designee immediately. Documentation with all relevant details will be completed to document the deviation and must be reported to the EC by the CM as required by local regulations.

The site will complete a protocol deviation eCRF form for all subject-related deviations and all deviations that are not related to a subject (for example, an untrained nurse performing investigational procedures) are reported in the Deviation Log by the PI.

If any deviations to the investigation plan are detected during the monitoring visit, the Monitor shall ensure the site reports all subject-related deviations in the eCRF and non-subject related deviations on the Deviation log in the Investigator Site File. Additionally, the monitor must report any deviation noted during the visit in the Periodic Monitoring Report.

14. Statement of compliance

The clinical investigation is conducted in accordance with:

- Ethical principles that have their origin in the Declaration of Helsinki, 1964, Last amended at the 59th WMA General Assembly, Brazil, October 2013.
- MDR (EU) 2017/745
- ISO 14155:2020 "Clinical Investigation of medical devices for human subjects Good clinical practices".
- Any applicable regional or national regulations will be specified in the country specific CIP.

14.1. Ethics committee and regulatory authorities

The CIP and/or other relevant documents are submitted to the appropriate EC and regulatory authorities. This clinical investigation will not begin until the required approval from the EC and regulatory authorities have been obtained. Any amendment to the protocol will be submitted to the same EC and regulatory authority.

Sponsor will notify the relevant regulatory authority and EC concerned of the end of the clinical investigation.

14.2. Data protection

As part of the investigation, Coloplast A/S. ("Coloplast") will collect and process the personal information the subject provides for the investigation ("subject personal data"). This includes identification and contact information (which may be anonymized depending on the nature of the investigation) as well as information about product usage experience and your health (sensitive data). Coloplast will comply with the EU General Data Protection Regulation (GDPR) and the Danish act on data protection ("databeskyttelsesloven"), including in connection with transfer of data to third countries, cf. chapter V of GDPR, Coloplast will only process the subjects' personal data:

- 1. To conduct the investigation and carry out related research based on subject voluntary consent (primary use), cf. articles 6(1)(a), cf. articles 9(2)(a) The EU's personal data regulation of GDPR.
- To comply with applicable legal obligations, which is the responsibility of Coloplast to e.g., ensure reliability and safety when processing clinical data, cf. article 6(1)(c) in conjunction with article 9(1)(i) of GDPR, and
- If separate consent is given for secondary use of subject personal data, cf. articles 6(1)(a) and 9(2)(a) of GDPR – carry out research outside the clinical protocol to improve Coloplast's products and services, and for use in education.

Part of Coloplast's processing is carried out on third-party platforms (clinical trial databases) and certain third parties are assisting Coloplast in the data processing (e.g., the PI). Such cases will imply a transfer of your personal data to the third parties (data processor), but solely for process data, for the specified purposes and with the third parties acting on instruction from Coloplast. Data may be collected and processed across the Coloplast network, which may entail processing of personal data outside the EU/EEA area. In such cases, an adequate level of protection will be ensured by the third parties being subject to the standard contractual clauses on data protection adopted by the EU or to an EU-approved certification mechanism on data protection officer (details below).

Subject personal data will be kept as long as required under applicable laws and regulations. The EU Medical Device Regulation obligates Coloplast to keep the data for a period of at least ten years after the investigation is completed, or, if the device is subsequently placed on the market, at least ten years after the last device has been placed on the market. Subject personal data will be deleted at the end of the mandatory retention period.

If the subject has questions or queries regarding Coloplast's handling of personal information, the subject can always contact Coloplast's Data Protection Officer at Complaints related to Coloplast's handling of subject personal information may similarly be sent to the Data Protection Officer, and the subject is also entitled to file a complaint with the relevant supervisory authority, which in the case of Denmark is the Danish Data Protection Agency (www.datatilsynet.dk).

The subject can write to request:

- Access to personal data.
- Correction of errors in personal data or to erase personal data.
- Limit what can be done with personal data.
- To receive personal data in machine-readable format (data portability).
- Withdrawal of consents the subject has given Coloplast to process personal data.

14.4. Financial conditions

Coloplast A/S will compensate all investigators involved in the clinical investigation for their time and resources spent on the investigation. All financial agreements with the investigation sites involved in the clinical investigation will be specified in a sponsor investigator agreement. None of the investigators has any financial relationship with sponsor outside the task of the clinical investigation activities.

15. Subject compensation

15.1. Compensation in case of injury

Product liability and No-Fault Clinical Investigation Insurance covering the duration of the clinical investigation are in place, to enable compensation in the event of an injury to a participating subject (see 15.3).

15.2. Disadvantage compensation for participating in the clinical investigation

Subjects will be compensated with a voucher per visit, paid by Coloplast A/S with the value as described in the Subject Information Form and in the table below:

Table 5: Disadvantage compensation

Visit	Disadvantage compensation
Visit 1 (V1)	
Visit 2 (V2)	

This is to compensate for any inconvenience caused during the TAI procedure and time used. There is no medical benefits for the subjects to participate in this clinical investigation, and even though subject are currently TAI users, there can still be some discomfort and pain. Travel expenses will be accounted separately. The vouchers are taxable (B-income), and it is the responsibility of the subject to declare this to SKAT.

16. Adverse events, adverse device effects and device deficiencies

16.1. Adverse events

An adverse event is any untoward medical occurrence, unintended disease or injury, or untoward clinical signs (including abnormal laboratory findings) in subjects, whether related to the investigational medical device(s) or the comparator(s), or the procedures involved. The adverse event shall be marked with the intensity mild, moderate or severe. This could include events such as headache or dizziness.

16.2. Adverse device effect (ADE)

An adverse event, which is related to the use of the investigational medical device, is an adverse device effect, and should be marked as unlikely related, possible related, probable related or with causal relationship on the adverse event form.

The definition of an adverse device effect includes any event resulting from insufficiencies or inadequacies in the instruction for use, deployment, implantation, installation and operation, or any malfunction of the medical device, as well as any event resulting from use error or from intentional misuse of the device.

If any adverse device effects occur for CE-marked Coloplast products the incident shall be stated in the Vigilance Form in the eCRF.

16.3. Device deficiency (DD)

A device deficiency is the inadequacy of the investigational medical device or comparator with respect to its identity, quality, durability, reliability, usability, safety or performance. This includes malfunctions, use errors and inadequacy in the information supplied by the manufacturer including labelling.

If any Device Deficiencies occur for CE-marked Coloplast products the incident shall be stated in the Vigilance Form in the eCRF.

Table 6: Examples of device deficiency

16.4. Serious adverse events (SAEs)

A serious adverse event is an adverse event that:

- 1. Led to death,
- 2. Led to a serious deterioration in the health of the subject, users or other persons as defined by one or more of the following:
 - o a life-threatening illness or injury, or
 - o a permanent impairment of a body structure or a body function including chronic diseases, or
 - o in-patient or prolonged hospitalization, or
 - medical or surgical intervention to prevent life-threatening illness or injury or permanent impairment to a body structure or a body function.
- 3. Led to foetal distress, foetal death, a congenital abnormality, or birth defect including physical or mental impairment.

This includes device deficiencies that might have led to a serious adverse event if:

- 1. Suitable action had not been taken, or
- 2. Intervention had not been made, or
- 3. Circumstances had been less fortunate.

These are handled under the serious adverse event reporting.

Planned hospitalization for a pre-existing condition, or a procedure required by the CIP, without serious deterioration in health, is not considered a serious adverse event.

16.4.1. Serious adverse device effect (SADE)

A serious adverse device effect is an adverse device effect that has resulted in any of the consequences characteristic of a serious adverse event.

16.4.2. Anticipated serious adverse device effect (ASADE)

There is no anticipated serious adverse device effect.

16.4.3. Unanticipated serious adverse device effect (USADE)

An unanticipated serious adverse device effect is a serious adverse device effect which by its nature, incidence, severity or outcome has not been identified in the current version of the risk analysis report.

16.5. Medical care of subjects

Principal investigator shall ensure that adequate medical care is provided, during and after participation in the clinical investigation, to a subject experiencing an adverse event. All ongoing ADEs, SAEs, SADEs and DDs that could have led to a SAE at subject termination will be followed according to the Risk Benefit analysis (see section 8.2). An ongoing adverse event at subject termination visit is documented as the current status for the adverse event and will not be followed up.

The subjects shall be informed of any new significant findings occurring during the clinical investigation, including the need for additional medical care that can be required, and of the nature and possible cause of any adverse events experienced.

16.6. Reporting and timelines

16.7. Investigator's reporting responsibilities

- PI at each site must assess all (S)AEs that occur at his/her site.
- All serious adverse events and serious adverse device effects must be reported to sponsor within 24 hours of the site becoming aware of the event.
- A device deficiency that could have led to a serious adverse event but did not because suitable action
 was taken, intervention had been made or because of fortunate circumstances should be reported to
 sponsor within 24 hours of the site becoming aware of the event.
- New findings and/or updates in relation to already reported serious events should also be reported to sponsor within 24 hours of the site becoming aware of the event.
- Device deficiencies and all adverse device effects related to CE-marked Coloplast investigational product and/or comparator must be reported to sponsor within 24 hours of becoming aware of the event.

When reporting the SAE, the relationship to the test material shall be described whether the event is considered:

- Not related, the event has no temporal relationship with the use of the test material or the procedures.
- Unlikely related, the relationship with the use of the test material seems not relevant and/or the event can be reasonably explained by another cause, but additional information may be obtained.
- **Possible related**, the relationship with the use of the test material is weak but cannot be ruled out completely. Alternative causes are also possible (e.g., an underlying or concurrent illness/ clinical condition or/and an effect of another device, drug or treatment). Cases where relatedness cannot be assessed or no information has been obtained should also be classified as possible.
- **Probable related,** the relationship with the use of the test material seems relevant and/or the event cannot reasonably be explained by another cause, but additional information may be obtained.
- Definitely related/Causal relationship, the event has a temporal relationship with the test material use/application or procedures.

And the intensity of the event should be considered, as such:

- Mild, the intensity of the event is mild with no further action or intervention.
- Moderate, the intensity of the event will lead to an action or intervention to solve the event.
- Severe, the intensity of the event will lead to follow up on the action or intervention, as the effect of the action or intervention may not decrease the symptoms.

All above events must be reported by use of the relevant adverse event/serious adverse event/device deficiency form.

Please report to:

Clinical Investigation Plan_

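### Section 16.7 defines *Not related* and *Definitely related* by timing alone, so an event during irrigation that is clearly due to another cause cannot be graded *Not related* and fits two opposing grades

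*Combined protocol and SAP*

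**What the plan says.** The scale in section 16.7 is introduced for serious events: "When reporting the SAE, the relationship to the test material shall be described whether the event is considered". It has five grades.

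- The lowest is "Not related, the event has no temporal relationship with the use of the test material or the procedures".
- The highest is "Definitely related/Causal relationship, the event has a temporal relationship with the test material use/application or procedures".
- The three between them (*Unlikely*, *Possible*, *Probable*) are described by how relevant or strong the relationship is and by whether something else explains the event. *Unlikely related*, for example, covers the case where "the event can be reasonably explained by another cause".

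Section 16.2 first defines an ADE as an adverse event related to use of the investigational device. It then says that such an event "should be marked as unlikely related, possible related, probable related or with causal relationship on the adverse event form". It neither defines these marks nor refers to section 16.7. Section 16.4.1 builds on this: "A serious adverse device effect is an adverse device effect that has resulted in any of the consequences characteristic of a serious adverse event".

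Some handling depends on ADE status. Section 16.5 follows up ADEs that are ongoing at termination, but not other ongoing non-serious adverse events. Section 16.7 says that "all adverse device effects related to CE-marked Coloplast investigational product and/or comparator must be reported to sponsor within 24 hours" of awareness. Section 16.2 adds: "If any adverse device effects occur for CE-marked Coloplast products the incident shall be stated in the Vigilance Form in the eCRF".

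**The concern.** A causality scale should place an event by how likely the device is to have caused it. Here the two ends are separated only by whether the event coincided with use of the product or the procedures, while the middle is ordered by cause. The ends and the middle can then give conflicting answers for the same event.

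The case that exposes this is an ordinary one: something happens during a supervised irrigation and has an evident, unrelated explanation. If timing alone bars such an event from *Not related*, and every other grade is an ADE mark, its classification as device-related rests on coincidence. Safety is the secondary objective of this first-in-human study, and about 20 subjects are to be randomised. One misgraded event would be conspicuous in any description of events by relationship.

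**Working it through.** No arithmetic applies. The check is to apply each definition to one test event: it occurs during irrigation and is clearly due to another cause.

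**Step 1: the five grades in section 16.7.**

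- *Not related*: requires the absence of a temporal relationship. The event happened during irrigation, so this is not met, whatever its cause.
- *Unlikely related*: asks whether the relationship seems irrelevant and/or another cause reasonably explains the event. Met.
- *Possible related*: asks for a weak relationship that cannot be excluded. Not a natural fit when the other cause is clear.
- *Probable related*: asks for a relevant relationship and/or no other reasonable explanation. Not met for this event.
- *Definitely related/Causal relationship*: the explanatory text asks only for a temporal relationship. The text is met, but the label is not.

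The event is therefore shut out of *Not related* and satisfies the text of two grades far apart on the scale. No other section adds a causal criterion to either end grade.

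**Step 2: the link to ADE status.** Section 16.2 can be read in two ways.

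- If its opening definition governs, an event must be related to the device to be an ADE, and the coincidental event is not one.
- If the marks govern, every grade from *unlikely* upward denotes an ADE. Only *Not related* lies outside, and Step 1 shows that this grade is closed to the event. The event is then an ADE or, if serious, a SADE under section 16.4.1.

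The plan does not say which reading applies.

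**Step 3: what would change.**

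- *Serious events.* Section 16.7 requires all SAEs to reach the sponsor within 24 hours. Section 16.8 requires all SAEs to reach the authorities within 7 calendar days. Section 16.5 follows up all ongoing SAEs. None of these depends on relatedness, so only the label (SAE or SADE) can change.
- *Non-serious events.* The scale is not introduced for them. If it is nevertheless used, and if the marks govern, ADE status could decide whether the event is followed up after termination. For CE-marked products it could also decide whether the 24-hour report and the Vigilance Form apply. The comparator, the gel and the irrigation system are all CE-marked. The investigational device is the non-CE-marked catheter together with the gel, and it is used with that system. What applies would therefore depend on the component to which the event is attributed.
- *Planned summaries.* Sections 5.3.4 and 10.1 provide for adverse events and device deficiencies. Neither count depends on the causality grade, and no ADE summary is specified.

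**The case against.** The strongest reply is that an investigator reads the label together with the text. The top grade is named *Causal relationship*, and section 16.2 uses that name as the mark. Nobody would give it to an event with an obvious other cause, and *Unlikely related* offers a suitable place. The remaining error is in the cautious direction. Section 16.2 also makes relatedness part of the definition of an ADE, so a coincidental event need not become one. The marks are made on an adverse event form that is not among the documents and may carry its own definitions. Section 8.4 provides for training of site staff in event reporting.

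Much of this stands. A reader might infer that the plan forces a coincidental event into *Definitely related*. It does not: *Unlikely related* is open, and the label discourages the top grade. A reader might also infer that every coincidental SAE becomes an unanticipated serious adverse device effect, because section 16.4.2 says that no serious device effect is anticipated. The documents do not support that either. It requires the marks to govern ADE status, and section 16.4.3 refers to a risk analysis report that is not in the documents.

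Two things survive the reply. No wording opens *Not related* to an event that coincides with irrigation, and the label of the top grade does nothing to cure that. Section 16.2 also leaves open whether *unlikely related* denotes an ADE, which is the question on which the consequence turns.

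On scope, the lead-in to the scale names only SAEs. Wider use is nonetheless plausible. Section 16.7 has the investigator assess serious and non-serious events alike. Section 16.1 requires an intensity grade for every adverse event, and the intensity definitions appear only in section 16.7, under the same lead-in. This makes wider use likely enough to clarify, but does not establish it.

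**Conclusion.** The point holds as a defect of wording with limited reach. Two of the five grades rest on timing alone. A coincidental event during irrigation cannot be graded *Not related*, and its text-based grade is ambiguous between *Unlikely* and *Definitely*.

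The step from there to ADE or SADE status is conditional on the marks in section 16.2 deciding that status. Any effect on the handling of non-serious events needs a further condition, namely that the section 16.7 scale is used for them.

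A reader might go further and conclude that expedited SAE reporting or the planned safety results are compromised. The documents do not support this, because neither the SAE duties nor the planned counts use the causality grade. What is exposed is the relatedness classification itself, and any breakdown by relationship that the report might add.

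The number of events affected cannot be given, because the plan states no adverse event rate. The conclusion assumes that the unseen adverse event form does not already supply better definitions. The change is desirable and nearly free, but not critical to the trial.

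**What to change.** First check whether the adverse event form carries its own definitions. Then:

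- In section 16.7, make *Definitely related* require a temporal relationship and the absence of any other reasonable cause.
- In section 16.7, let *Not related* include events clearly due to another cause, whatever their timing.
- In section 16.2, refer to section 16.7 for the meaning of the marks, and reconcile the ADE definition with the *unlikely related* mark so that it is clear which decides ADE status. The lead-in in section 16.7 should then state which events the scale covers.
- Align the adverse event form if it repeats the present text.

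The cost is a change of wording in two sections and possibly one form, handled under the amendment procedure in section 12. It needs no extra subjects, visits or data fields.
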